### 6.2 Details of Measurements

## 6.2.1 Questionnaires

Most questionnaires will be administered at baseline and at the F4 and F12 visits (Table 11 A). Because self-administered questionnaires may be more difficult to complete for the elderly, minority groups, and those with high comorbidity from trial participation [Unruh, 2003], all questionnaires will be administered by trained interviewers blinded to treatment allocation through a central telephone core. Questionnaires that cannot be administered by telephone due to the need for visual cues (i.e., Feeling Thermometer, Trail Making B, and Modified Mini-Mental Status) will be administered by the local study coordinator.

# 6.2.2 Objective Tests of Physical Function

The Lower Extremity Battery (LEP: timed 8-foot walk, timed chair stand, and balance test) will be performed at baseline, and at the F4 and F12 visits (Table 11 A). These tests will be conducted by the study coordinator before the HD session since performance scores can be affected after a single HD treatment [Tawney, 2004]. The study coordinators will be trained by an experienced person familiar with the methods of these tests prior to study start.

For the LEP, performance scores will be derived for each test with a score of 0 assigned to those unable to complete the test, and 4 indicating the highest level of performance. Ordinal categories for the 8-foot walk, chair stand, and balance test will be assigned based on reference tables developed for elderly people who participated in the EPESE study [Guralnik, 1994]. In addition, the individual scores for each of the 3 tests will be summed to create an overall LEP score (0-12). The LEP score incorporates missing data into the test results by assigning a score of 0 for missing values and for those unable to complete the test, while those who are able to complete the test are assigned a score according to a quartile of performance.

# 6.2.3 Local Laboratory Measurements from Kinetic Modeling Sessions

Blood will be drawn pre and post-dialysis at each kinetic modeling session. Samples will be refrigerated and then shipped to the local laboratory associated with the dialysis unit. See Section 6.1 and Table 11 B for frequency with which various labs will be drawn. In addition, at baseline, and at the F4 and F12 visits, the patient's urine will be collected for the period in between HD sessions along with the time of collection for assessment of urea, creatinine, and phosphate excretion rates.

### Table 11. Summary of Data Collection Schedule

Measurement	Central Telephone Interview	Baseline	1 mo	2 mo	3 mo	4 mo	5 mo	6 mo	7 mo	8 mo	9 mo	10 mo	11 mo	12 mo
SF-36 Survey, v1	Yes	~				√								$\checkmark$
Health Utilities Index –3	Yes	~				✓								$\checkmark$
Feeling Thermometer	No	~				✓								$\checkmark$
MOS Sleep Scale	Yes	~				~								✓
Beck Depression Inventory, v1	Yes	~				✓								$\checkmark$
Trail Making B	No	~				✓								$\checkmark$
Modified Mini Mental Status	No	~				✓								$\checkmark$
Physical Function	No	~				✓								✓
Cousineau – Burden QoL	Yes	~				✓								✓

A. Health-related Quality of Life/Physical Function, Depression, Cognitive Function, and Treatment Burden Measures; and Characterizing Non-dialytic Aspects of the Intervention

\*All physical and cognitive testing to be done pre-dialysis, mid-week within 2 weeks of scheduled time.

### **B.** Laboratory Measurements and Medications

Measurement	Baseline	1 mo	2 mo	3 mo	4 mo	5 mo	6 mo	7 mo	8 mo	9 mo	10 mo	11 mo	12 mo
Predialysis serum albumin	~~	~	~	~	~	~	~	~	~	~	~	~	✓
Pre and post-dialysis serum phosphate, creatinine, urea	~~	~	~	~	~	~	~	~	~	~	~	~	√
Interdialytic urine for urea, creatinine, phosphate	~				~								√
Pre-dialysis hemoglobin, calcium, bicarbonate, sodium, and potassium	~	~	~	~	~	~	~	~	~	~	~	~	✓
Pre-dialysis transferrin and ferritin 	~			✓				✓				✓	
Pre-dialysis parathyroid hormone 	~			√				✓				✓	
Intravenous iron (cumulative monthly dose)	~	~	~	~	✓	~	~	~	~	~	~	~	~
Erythropoietin/Darbopoetin (route, frequency, weekly dose, cumulative monthly dose)	V				~				✓				~
IV vitamin D metabolites (frequency, weekly dose)	~				✓				~				~
Phosphorus binders (daily dose)	✓				~				~				✓
All other medications (including antihypertensives)	~				✓				~				✓
Serum/plasma samples for biorepository	~				~								~

These local labs to be entered into database at least once every 4 months (center may optionally enter these labs at additional time points) FHN Daily Protocol Version 2.3.1: July 2, 2008 40

#### C. Cardiovascular, Blood Pressure, and Nutritional/Inflammatory Measures (for labs and medications, see above)

Measurement	Blinded Reading	Baseline	1 mo	2 mo	3 mo	4 mo	5 mo	6 mo	7 mo	8 mo	9 mo	10 mo	11 mo	12 mo
Cardiovascular Measures														
Cardiac cine-MRI	Yes	✓												~
24-hour Holter monitoring (heart-rate variability)	Yes	✓												~
Predialysis and postdialysis systolic and diastolic blood pressures*	No	~	~	~	~	~	~	~	~	~	~	~	~	~
Predialysis and postdialysis weight*	No	✓	~	~	~	~	~	~	~	~	~	~	~	~
Interdialytic hypotensive episodes*	No	~	~	~	~	~	~	~	~	~	~	~	~	~
Nutritional Measures														
Protein catabolic rate	Yes	✓	~	~	~	~	~	~	~	~	~	✓	~	~
Bioelectric impedance	No	✓	~			~								~

\*These measures taken at each kinetic modeling session. Additional measurements from dialysis sessions over the prior 1-week interval also recorded once during baseline and monthly during follow-up.

### D. Mineral Metabolism and Anemia Measures – see Labs and Medications Table 11B

E. Events (hospitalizations, access complications, survival, and discontinuation of intervention) will be collected throughout follow-up

# F. Treatment Burden, and Characterizing the Non-dialytic Aspects of the Intervention

Measurement	Baseline	1 mo	2 mo	3 mo	4 mo	5 mo	6 mo	7 mo	8 mo	9 mo	10 mo	11 mo	12 mo
Adherence to Therapy						-							
Number of missed sessions (over 1 month)		~	~	~	~	~	~	~	~	~	~	~	✓
Number of shortened treatments (over last week as needed)		~	~	~	~	~	~	~	~	~	~	~	✓
Central` QoL- Burden of Treatment													
Minutes to recovery question	√				✓								✓
Modality preference question	~				~								✓
Characterizing the Non-dialytic aspe	ects of the I	nterve	ntion										
Time spent with health-care	1				~								~
Frequency of reductions to ideal weight prescriptions		1			✓								✓
Frequency/method of vascular access monitoring PRN		~			~								✓
Compliance to medications question		~			✓								✓

It is recommended that serum albumin be measured using the bromcresol green assay, as this is the most widely used measure of albumin in the U.S. Laboratory parameters which are not obtained as part of the dialysis units usual patient care will be specifically ordered, and costs paid by the Study.

# 6.2.4 Medications

Study coordinators will verify that the medications correspond to the prescribed medication list prior to data collection and entry. All prescribed medications (except intravenous iron, erythropoeitin/darbopoetin, and intravenous vitamin D metabolites) will be recorded with daily doses using the WHO DRUG system at baseline and at the F4, F8, and F12 visits. For vitamin D metabolites, the frequency and total weekly dose will be recorded. For erythropoeitin/darbopoeitin, the frequency and total weekly dose, along with the cumulative dose over the last 4 weeks will be recorded. Intravenous iron use will be recorded monthly, as the cumulative dose over the prior 4 weeks. Please see Table 11 B.

# 6.2.5 Cardiac MRI

The cardiac Magnetic Resonance Imaging (MRI) study will be performed at baseline and at the F-12 visit (Table 11 D). The most commonly used method to measure LVM is two-dimensional (2D) doppler echocardiography. Since the method assumes a geometric shape of the normal heart, it is less accurate for dilated or extremely hypertrophic hearts. Furthermore, the results are heavily operator dependent and the variability of the measurement for LVM was found to be wider than originally thought [Collins, 1989; Palmieri, 1999]. Cine-MRI has been shown to be more accurate and less volume and operator dependent than 2D-echocardiography. Cine-MRI assessment of LVM showed a good interstudy reproducibility of 7.8 g (mean weighted values from 11 studies), intraobserver reproducibility of 4.8 g, and interobserver reproducibility of 9.0 g in mainly normal subjects. This is contrasted by a mean weighted interstudy SD for 2D-echo of 19.2 g [Myerson, 2002]. Moreover, in addition to determination of LVM, the cine MRI technology allows for measurement of various cardio-dynamic parameters, such as end-diastolic volume (EDV), end-systolic volume (ESV), stroke volume, ejection fraction, myocardial mass and cardiac output [Kramer, 2004]. We suspect that the relative superiorities of MRI over echocardiography are compounded in ESRD patients who not only have a high prevalence of left ventricular hypertrophy, but who also suffer from volume expansion between HD sessions [Stewart, 1999]. For these reasons cardiac cine MRI will be used for the assessment of LVM in all study patients.

Availability of MRI centers experienced in performing standard cine-MRI examinations has been verified by the study Clinical Centers using a standardized questionnaire. MRI scans will be performed at designated MRI centers close to each patient's study HD unit. Scans will be digitized and provided to a Central MRI reading center where they will be analyzed in a standardized way by a trained person, blinded to the patient's treatment allocation.

# 6.2.6 Heart Rate Variability/Holter Monitoring

Heart rate variability will be measured at baseline and at the F12 visit using 24-hour Holter measurements from KCI (Table 11 C). Holter at baseline is not required for randomization.

It is recommended, if possible, for Holter monitoring to be done on the first dialysis day following the weekend. Each 24-hour Holter analysis period will commence immediately after placement of the Holter equipment, which will take place at any point in time in the hour proceeding the start of dialysis.

Analysis will be carried out for three periods:

Period 1: the time between placement of the Holter and the end of the dialysis session,

Period 2: the time between the end of the dialysis session and starting time + 12 hours,

Period 3: the time between the end of Period 2 and starting time + 24 hours.

Each study site will download the data onto CD and send to the core lab, where data will be analyzed by a trained person blinded to the patient's treatment allocation.

# 6.2.7 Blood Pressure, Interdialytic Weight Gains, and Intradialytic Hypotensive Episodes

Pre and post-dialysis systolic and diastolic blood pressures, the nadir recorded intradialytic systolic and diastolic blood pressures, pre and postdialysis weights, and the presence of intradialytic hypotension requiring intravenous saline will be recorded from the HD run sheets for each HD session over a 1-week interval prior to and including the kinetic modeling session once during baseline and monthly during follow-up. In other words, these measures will be recorded for 3 sessions in the conventional arm, and at most for 6 sessions in the daily arm. Interdialytic weight gains will be calculated from the pre and post weights. See Table 11 C.

# 6.2.8 Bioelectric Impedance

Single frequency bioelectric impedance (BIA) assessments should be performed at baseline and at the F1, F4, and F12 visits. The baseline measure is not required for randomization. All measurements should be conducted in the recumbent position, and should be performed immediately prior to a mid-week HD treatment (i.e., Wednesday or Thursday). BIA should not be performed on bilateral amputees or who have metallic implants such as a pacemaker.

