#### 2.4 Recruitment Strategy

The target sample size for this trial is 250 subjects, half of whom will be randomized to in-center daily HD. Subjects will be recruited from dialysis units associated with designated Clinical Centers affiliated with the two Consortium Cores. Within each of the Clinical Centers, persons receiving conventional 3 times weekly HD in the associated HD units will be potential study subjects. Currently, these dialysis units provide clinical services to > 7500 prevalent HD patients. It is estimated that approximately 50% of prevalent HD patients will be eligible for enrollment, based on inclusion and exclusion criteria. Resource and logistical constraints (e.g., available stations) may limit the numbers of subjects for whom the protocol can be implemented concurrently at a given site. Local efforts will be concentrated on those dialysis units and referring nephrology programs with large numbers of patients and adequate physical space. Under this staggered enrollment strategy, fewer than 50% of the total number of randomized subjects will be in the trial at any given time, thus easing the time required to implement the protocol for personnel conducting the study.

The progress of recruitment into this trial and into the companion nocturnal dialysis trial will be reviewed by the Data Safety and Monitoring Board (DSMB) at the conclusion of the one year Vanguard phase. Depending on the progress of the two trials, their target sample sizes may be modified.

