# Other Secondary Outcomes:

Outcomes based on the Cardiac MRI: In addition to determination of LVM, the cine-MRI technology allows for measurement of various cardio-dynamic parameters, such as end-diastolic volume (EDV), end-systolic volume (ESV), stroke volume, ejection fraction (EF), and cardiac output

(CO). Some of these measures are influenced by volume status (EDV, ESV), whereas others are indicators of cardiac function and atherosclerotic changes (stroke volume, EF, and CO). The 12-month change in each of these parameters will be used as additional secondary outcome parameters.

Heart Rate Variability. The heart rate is naturally quite variable, and mathematical analysis of variability of beat-to-beat intervals reveals both high and low frequency components which have been linked to the degree of parasympathetic and sympathetic tone. Heart rate variability (HRV) also has a structural component, and has been shown to be markedly reduced in CHF and in LVH [Nishimura, 2004]. Reduced HRV also has been linked to diabetic autonomic neuropathy. HRV may be a surrogate outcome for mortality [Adamson, 2004;Wichterle, 2004].

Category	Outcome
Co-Primary Outcomes:	
Cardiovascular Structure and Function	Composite of 12 month Mortality and change in Left-Ventricular Mass by Cine-MRI
Health-related Quality of Life and Physical Function	Composite of 12 month Mortality and change in SF-36 Physical Health Composite Score
Secondary Outcomes: ( 9 dom domain)	nains – those in bold are designated as main "priority" outcomes within the
Cardiovascular Structure and	Left-ventricular mass by cine-MRI
Function	End-diastolic, end-systolic, and stroke volumes, ejection fraction, cardiac output
	Heart rate variability measures
	Rate of intradialytic hypotension episodes
	Interdialytic weight gain
Health-related Quality of	SF-36 Physical Health Composite score
Life/Physical Function	Health Utilities Index score
	Feeling Thermometer score
	Medical Outcomes Study Sleep Scale
	Lower Extremity Performance Battery* score
Depression/Burden of Illness	Beck Depression Inventory score
Cognitive Function	Trail Making B score
	Modified Mini-Mental Status score
Nutrition and Inflammation	Serum albumin
	Normalized protein catabolic rate
	Body mass index

	Lean body mass by single frequency bioimpedance analysis
Mineral Metabolism	Predialysis serum phosphate
	Predialysis serum calcium
	Calcium-phosphate product
	Parathyroid hormone
	Phosphate binder dose

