Intradialytic Hypotension: Intradialytic hypotensive episodes (IDHE) occur in approximately 20% of standard 3x/week dialysis treatments [Kyriazis, 2004]. In addition to complicating delivery of an adequate treatment and reducing patients' quality of life, repeated IDHE may cause ischemia to critical body organs, including brain, heart, intestines, and thereby contribute to an increased risk of hospitalization and death [Ishida, 1999]. IDHE has been associated with mortality in HD patients [Shoji, 2004;Tisler, 2003]. Due to a shorter interdialytic interval, daily HD results in lower ultrafiltration rates provided total daily fluid intake remains constant or minimally increased. It is thus hypothesized that daily HD will reduce the rate of IDHE, as suggested by some observational studies [Heidenheim, 2003].

Interdialytic Weight Gain: Absolute interdialytic weight gains correlate with pre-dialysis blood pressure. A decrease in interdialytic weight gain has been hypothesized to be one mechanism by which LVMi and blood pressure may improve. In previous observational studies, absolute weight gains between dialysis sessions have decreased with daily HD due to halving of the interdialytic interval, but in fact cumulative weekly gains have tended to increase [Andre, 2002b;Fagugli, 2001;Galland, 2004a;Kooistra, 1998;Nesrallah, 2003;Ting, 2003]. Thus, in this trial, both the 12-month changes in mean interdialytic weight gain between dialysis sessions, as well as in cumulative weekly weight gains will be assessed as additional secondary outcomes.

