#### Other Secondary Outcomes:

It is recognized that potential increases between baseline and 12 months in serum albumin may be the result of reductions in extracellular volume with daily HD rather than an improvement in inflammation or nutrition. For this reason, the change between 1 and 12 months is defined as an additional secondary outcome as any increases in serum albumin solely due to reduced extracellular fluid volume would be expected to occur by 1-month post-randomization.

No nutritional parameter rivals serum albumin in terms of predictive power for outcomes such as mortality and hospitalization. However, serum albumin reflects both inflammation as well as nutrition, and it may be influenced by volume status. In addition, nutritional status extends beyond the visceral protein pool. Unfortunately, there is no ideal true nutritional marker, due to the lack of a single measure that is easily performed, reproducible, inexpensive, and able to predict hard outcomes. Most studies rely on a combination of measures to assess nutritional status. For this trial, the 12 month change in the normalized protein catabolic rate, post-dialysis body mass index, and lean body mass by single frequency bioimpedance have been chosen as additional secondary nutritional outcomes. Since poor appetite and altered body composition are observed frequently in patients with FHN Daily Protocol Version 2.3.1: July 2, 2008 31

advanced chronic kidney diseasewith evolving uremia, we hypothesize that daily HD might improve these parameters due to increased clearance of uremic toxins.

Normalized Protein Catabolic Rate (nPCR): The nPCR has been used in dialysis patients for decades as an estimate of dietary protein intake [Gotch, 1995]. The use of the nPCR assumes, however, that the patent is in neutral nitrogen balance, an assumption that is not always met in conventional HD patients. Moreover, the agreement between nPCR and true dietary protein intake has not been assessed for daily HD patients. Despite these concerns, the nPCR has been chosen as a measure of dietary protein intake in this trial because of budgetary constraints and ease of measurement of nPCR compared to dietary records, interviews by dieticians, and food frequency questionnaires.

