### 9.5 General Analytic Strategy for Quantitative Outcomes

The following analytic strategy will be employed for quantitative outcomes, including each of the main secondary outcomes with the exception of the rate of nonaccess hospitalization or death. The main analysis for each outcome will evaluate the treatment effect on the change from baseline to 1 year. For outcomes evaluated monthly (e.g., serum albumin and pre-dialysis phosphorus), the baseline value will be averaged over two baseline assessments and the 1 year value will be averaged over the Month 10, 11, and 12 assessments for increased statistical power. For each outcome with multiple follow-up assessments (including the PHC, serum albumin, Beck Depression Inventory, Trail Making Test B, and pre-dialysis phosphorus), an additional analysis will be conducted to evaluate the change from baseline to Month 4, where the Month 4 value is taken as the average value over months 3, 4, and 5 for serum albumin and pre-dialysis phosphorus. The analysis of change to 4 months will evaluate short term effects, while the analysis of change to 1 year will evaluate longer-term effects. The 4-month comparison is also intended to evaluate treatment effects prior to significant attrition. The "basic model" to be used for quantitative outcomes is:

$$\Delta Y_{t} = \beta_{0t} + \beta_{1t} \operatorname{Trt} + \beta_{2t} Y_{0} + \Sigma \gamma_{it} S_{i} + \Sigma \delta_{it} F_{i} + \varepsilon_{t}, \qquad (Basic Model)$$

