## 9.8 Additional Analyses of the Effects of the Interventions

In addition to considering effects of the interventions on outcome at 4 and 12 months, contrasts will be constructed to estimate their effects on the change from 4 to 12 months to determine if treatment effects are changing over time. For quantitative outcomes obtained monthly, the basic model will be extended to evaluate patterns of change incorporating each protocol time point. Due to the larger number of time points, the covariance matrix of the residuals will be estimated under a mixed effects model including random effects (e.g., a random intercept and slope) and additional correlation parameters as needed to fit the serial correlation structure of the data [Littell, 1996;Verbeke, 1998].

Concentrations of serum albumin, hematocrit, and hemoglobin as well as blood pressure and body weight may shift shortly after initiation of daily dialysis due to altered extracellular volume, complicating interpretation of longitudinal changes. Thus, we plan to supplement tests of effects of the treatment interventions on changes from baseline to month 4 or month 12 (which may overestimate beneficial effects of the daily intervention due to hemoconcentration) with contrasts evaluating the changes from the month 1 visit, at which time most hemoconcentration effects should have occurred. Contrasts for changes from baseline to the month 1 visit will be used to estimate the size of the change in extracellular water and the associated hemoconcentration effects.

Analyses will also be used to test for interactions between the treatment interventions and prespecified baseline factors to evaluate whether certain subgroups experience increased or reduced benefits of the interventions. The Steering Committee has pre-specified the following factors for evaluation of treatment interactions:

History of heart disease, gender, anthropometric volume (Watson volume < 35 L vs.  $\ge 35$  L), years of dialysis (< 4 years vs.  $\ge 4$  years), presence of residual renal function (defined by > 100 mL urine volume per 24 hours).

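### Pre-dialysis bioimpedance biases the baseline-to-12-month lean-mass change toward apparent loss on daily HD, and the month-1-to-12 contrast that would reveal this is not assigned to lean mass

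*Protocol*

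**What the plan says.** - **Timing.** Section 6.2.8 schedules single-frequency BIA at baseline, F1, F4 and F12 in both arms, and says it "should be performed immediately prior to a mid-week HD treatment".
- **Schedule at baseline.** Under 2.4, "persons receiving conventional 3 times weekly HD in the associated HD units will be potential study subjects". After randomization the daily arm moves to six sessions a week (3.1.1).
- **Outcome and contrast.** Table 10 lists "Lean body mass by single frequency bioimpedance analysis" under Nutrition and Inflammation. Section 5.1.3.5 defines the additional nutritional outcomes as "the 12 month change in the normalized protein catabolic rate, post-dialysis body mass index, and lean body mass by single frequency bioimpedance". Section 9.5 says of quantitative outcomes: "The main analysis for each outcome will evaluate the treatment effect on the change from baseline to 1 year".
- **Fluid.** Section 5.1.3.1 reports from earlier studies that "absolute weight gains between dialysis sessions have decreased with daily HD due to halving of the interdialytic interval", and adds that weekly totals tended to go up. Section 5.1.3.5 says BIA will be used to estimate body water and cell mass, treats excess fluid as a confounder of BMI, and bases BMI on post-dialysis weight.
- **Safeguards.** Section 6.1 explains the extra F1 BIA reading as a way to show early volume effects. Section 9.8 warns that "Concentrations of serum albumin, hematocrit, and hemoglobin as well as blood pressure and body weight may shift shortly after initiation of daily dialysis", supplements those analyses with contrasts from month 1, and uses baseline-to-month-1 contrasts to size the change in extracellular water. Section 5.1.3.5 makes the month-1-to-12 change an additional outcome for albumin. Neither section names lean body mass.

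**The concern.** Treatment changes the conditions under which the outcome is measured. A control patient is read after the same interval at baseline and at F12, so accumulated fluid cancels in the change score. A daily-arm patient is read after an interval about half as long at F12 as at baseline. If lean mass is derived from BIA body water, the absent fluid is counted as lost lean tissue in that arm only. Randomization does not remove this, because the shift is a consequence of assignment.

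The bias runs against the hypothesis in 5.1.3.5 that daily HD might improve body composition. It could mask a true gain, or be read as support for the malnutrition risk raised in 5.2.3. BMI is protected by its post-dialysis weight and albumin by its month-1 contrast. Lean mass has neither in the text, although its F1 reading is collected.

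**Working it through.** **1. Reproduce the plan's intervals (Table 3).** Interval = time between session starts minus session length, with median sessions of 3.50 h (conventional) and 2.36 h (daily), and 10.5 and 14.2 h per week.

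- Maximum: 72 − 3.50 = 68.5 h and 48 − 2.36 = 45.64 h (stated 68.5 and 45.6).
- Average: (168 − 10.5)/3 = 52.5 h and (168 − 14.2)/6 = 25.63 h (stated 52.5 and 25.6).

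All four agree.

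**2. Apply the same rule to the mid-week reading.**

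- Three sessions a week: 48 − 3.50 = 44.5 h.
- Six sessions a week: 24 − 2.36 = 21.64 h.
- Ratio: 21.64/44.5 = 0.486.

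If a daily patient's day off fell just before the reading, the interval would be 48 − 2.36 = 45.64 h and this shift would vanish. The protocol does not fix the day off.

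**3. Missing water at F12.** The protocol gives no interdialytic gain. Assume a mid-week gain G of 1.5 to 3.0 L on conventional HD. Because 5.1.3.1 says weekly gains tended to rise on daily HD, let them rise by u = 0 to 30% (also assumed). Missing water = G × [1 − 0.486 × (1 + u)].

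- Low end: 1.5 × (1 − 0.632) = 0.55 L.
- High end: 3.0 × (1 − 0.486) = 1.54 L.

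**4. Apparent lean-mass loss.** No lean-mass equation is given, so two conversions are assumed.

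- Half of the water read as lean tissue: 0.5 × 0.55 = 0.28 kg to 0.5 × 1.54 = 0.77 kg.
- Lean mass taken as water/0.73: 0.55/0.73 = 0.76 kg (unrounded inputs) to 1.54/0.73 = 2.11 kg.

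Overall, about 0.3 to 2.1 kg.

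**5. Would it be noticed?** With 250 randomized 1:1 and 80% measured at 12 months (9.11), about 100 per arm are analysed. As a check on this frame, (1.96 + z) × √(2/100) gives 0.396 SD at 80% power and 0.458 SD at 90%, against 0.40 and 0.46 in Table 15b. The SD of the 12-month lean-mass change is not stated; 2 to 5 kg is assumed. With no true effect, the probability of declaring a significant loss is Φ(bias/(SD × √(2/100)) − 1.96):

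| Bias | SD 2 kg | SD 3 kg | SD 4 kg | SD 5 kg |
|---|---|---|---|---|
| 0.5 kg | 0.42 | 0.22 | 0.14 | 0.11 |
| 1.0 kg | 0.94 | 0.65 | 0.42 | 0.29 |

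The nominal rate in that direction is 0.025.

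**6. What a month-1 start does.** The daily schedule applies at both F1 and F12, so the interval term largely cancels. It does not cancel fully for patients who step down in frequency between those visits under Table 7.

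**The case against.** The strongest reply is that the protocol already sees the problem. The F1 BIA was added to show volume effects, and 9.8 already sizes the early change in extracellular water. BIA is the body-water measure scheduled at that visit, so the fluid effect can be separated from data already planned. That stands: a reader might infer that the plan overlooks fluid in its BIA data, and it does not. What remains is narrower. The contrast stated for lean mass is baseline to 12 months, and lean mass is not named for a contrast from month 1.

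A second reply is that supplementary contrasts belong in an analysis plan. This has some force, but the protocol itself fixes the reading time and the 12-month change, and lists the outcomes that get the month-1 treatment.

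Third, the outcome is low in the hierarchy. Section 9.4 treats non-main outcomes within a domain as exploratory, and the nutrition domain is judged on albumin. That stands and limits the weight of the point. It also weakens a safety reading. Nutritional status under 5.2.3 is followed through several measures, and BIA is not among the annual safety summaries listed in 10.2.

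Finally, one might infer that month 1 to month 12 should become the main lean-mass contrast. The protocol does not go that far for albumin, where the month-1 contrast is an addition. Doing so would also make a post-randomization value the starting point of the main analysis.

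**Conclusion.** The point holds as a bias in one exploratory outcome. Following the plan as written, the baseline-to-12-month change in BIA lean body mass is biased toward loss in the daily arm, because the interval before the reading drops to about 0.49 of its baseline length there and does not change in controls. The direction assumes that lean mass is derived from BIA water, which 5.1.3.5 supports without giving an equation, and that the day off does not precede the reading.

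The size cannot be computed from the document. The range of roughly 0.3 to 2.1 kg rests entirely on the assumed gain, the assumed rise in weekly gains and the assumed conversion. A reader might infer that the trial will show a spurious loss. The documents do not support that, since a true gain could offset the bias and its size is unknown. Any real fall in post-dialysis fluid volume would add to the bias in the same direction and is not part of this range. The co-primary and main secondary outcomes are not affected.

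**What to change.** In 5.1.3.5 and 9.8, add BIA lean body mass and the other BIA outcomes to the pre-specified month-1-to-month-12 contrasts, as is done for albumin. Report that contrast beside the baseline-to-12-month change. State in advance that a baseline-to-12-month loss in the daily arm that is not confirmed from month 1 is to be read as a fluid effect.

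The cost is wording and one additional analysis, since the F1 reading is already scheduled. The downside is that true lean-mass change in the first month is not credited in the added contrast, and a real early loss could be attributed to fluid. Keeping both contrasts in the report makes that visible.
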